3.	The POMS (Grocott MP et al)	34
4.	Non-cardiac surgeries routinely requiring invasive monitoring:	35

TRIAL SUMMARY

Design: Single-center randomized comparison of invasive arterial pressure monitoring vs. arterial pressure monitoring combined with Acumen Hypotension Prediction Index (HPI) software guidance on intraoperative hypotension duration and severity.

Anticipated enrollment period: 12 months

Aim: To determine whether use of Acumen HPI software guidance to guide intraoperative hemodynamic management in the non-cardiac surgery reduces the duration and severity of hypotension.

Primary hypothesis: Our primary hypothesis is that adding Acumen HPI software guidance to the information provided by the invasive arterial pressure monitoring during moderate- to high-risk noncardiac surgery reduces time-weighted average (TWA) intraoperative hypotension below a threshold of 65 mmHg.

Outcomes:

Primary

1. Time-weighted average MAP below a threshold of 65 mmHg per case.

Secondary

- 1. Time-weighted average MAP below a threshold of 60 mmHg per case;
- 2. Time-weighted average MAP below a threshold of 55 mmHg per case.

Exploratory

- 1. A collapsed composite of non-fatal cardiac arrest, in-hospital death, stroke, and MINS;
- 2. Acute kidney injury (AKIN criteria);
- 3. Quality of recovery (QoR-15) on postoperative day 3;
- 4. Postoperative morbidity survey (POMS) on postoperative day 3;
- 5. Transfusion requirement (ml packed red blood cells);
- 6. Amounts of intraoperative crystalloid and colloid;
- 7. Amount of vasopressors phenylephrine, ephedrine, nor-epinephrine, epinephrine, dobutamine;
- 8. Advanced hemodynamic variables- Cardiac output (CO), Cardiac Index (CI), Stroke Volume (SV), Stroke Volume Variation (SVV);
- 9. Hospital length of stay;
- 10. Hospital readmission within 30 days.

Sample size: 213.

INTRODUCTION

In 2012, the global volume of surgery was estimated to be 312 million operations, a 33% increase from 2004.¹ According to Weiser et al, the increase in surgical volume is projected to grow with economic development. Surgery is associated with high mortality and morbidity, despite substantial improvements in technical expertise and patient monitoring. Overall inpatient 30-day mortality is about 2%, and climbs up to 6% in high-risk populations.²⁻⁷ More than 1% of patients aged 45 years or more die after major non-cardiac surgery while in the hospital or within 30 days of surgery.⁸

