The amount and timing of intravenous fluids and vasopressor drugs will be decided by the anesthesia team based on the guidance from the software in the intervention group. The software provide multiple parameters. In order to standardize the interpretation of hemodynamic parameters clinicians at Cleveland Clinic has agreed to the conceptual framework presented in Figure 6. In the arterial pressure monitoring group without Acumen HPI, clinicians will make treatment decision based on the pressure waveform. In all cases, good clinical judgment will be predominant, and the attending anesthesiologist take all necessary steps to provide optimal and safe care. Blood and blood products will be administered based on clinical judgment.

[figure not shown]

Figure-6 Conceptual framework for the hemodynamic management

A research fellow will be present in the operating room and will monitor the HPI value and the response by the clinical team every 15 min and also when HPI >85. He will specifically document the HPI number and the hemodynamic state – hypovolemia, vasoplegia and decreased contractility and document the clinician's response as following

Table 1- Intraoperative data collection

Time stamp	HPI value	Hemodynamic state per clinical team	Hemodynamic state per Acumen HPI
1.			
2.			
3.			
4.			
5.			

Blinding

Patients will be blinded to group allocation. Anesthesiologist, surgeons, data gathering research personnel and operating room team cannot be blinded to the treatment arm. Principal investigators, co-investigators and the data analysis team will be blinded for the treatment groups. The amount and timing of intravenous fluids and vasopressors will be decided by the anesthesia team based on the clinical assessment which is current standard of care.

Postoperative Management

The attending anesthesiologists and surgeons, taking into account the clinical condition of individual patients and risk of complications, will determine whether postoperative ICU admission is appropriate.

Measurements

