Summary. From our a-line study [unpublished] we observed mean (SD) of area under the curve AUC-MAP<65 of 80 (127) and median [quartiles] of 24 [1, 121]. Similar to time weighted average AUC-MAP represents depth and duration of hypotension. AUC-MAP = TWA-MAP x duration of observation. The data is highly skewed, with a non-trivial proportion of zeros. Therefore, it is not appropriate to base a sample size estimate on a t-test which assumes normality. It is best based on a non-parametric test such as the Wilcoxon-Mann-Whitney test, as put forth in the preliminary protocol for the larger study. In that study we needed about 800 patients to detect a 50% reduction in the median, based on 90% power and incorporating interim analyses. For the calculations below we use 80% power. As noted below, for the current study we recommend a total sample size of 213 to detect an approximate 20% reduction in the mean of the primary outcome of AUC-MAP < 65 mmHg x min, which based on the pilot data corresponds to a Wilcoxon-Mann-Whitney probability (i.e., a c-statistic) of 0.61.

Detailed calculations. In the below Table 3, using the same calculations based on the Wilcoxon-Mann-Whitney test as in the proposal for the larger HPI trial, we present the required sample size to detect reductions or shifts in the distribution of the primary outcome (AUC-MAP < 65 mmHg x min) which are equal to various percentages (*achieved* reductions ranging from 7% to 35%) of the control group mean. The reduction is applied on a case level (i.e., for each control observation), so that a reduction of say 10% of the mean would reduce all observations by 8 mm Hg x min (0.10 x control group mean (80 mmHg x min). But if that brings an observation below zero, the value of zero is used (cannot have negative AUC!). Table 3 thus gives a top row for the *attempted* reduction (on the case level), and then the *achieved* HPI mean and median, as well as the ratio (HPI/control) of means and medians.

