Recommended Sample Size of total N=213: In the 35% attempted reduction column, a reduction of 35% of the control mean (equal to 28 mmHg x min) was *attempted* for all control cases when constructing the HPI distribution of outcomes. The *achieved* ratio of means was 0.79, indicating a 21% reduction in the mean. The achieved reduction was not the full 35% since, as expected, many of the cases reached zero instead of the full attempted reduction. This scenario also brought the HPI median (and thus the ratio of medians) to zero. The scenario requires a total of 213 patients (107 / group). The Wilcoxon-Mann-Whitney probability of 0.61 means the probability that randomly chosen HPI patient has lower AUC-MAP<65 compared to random control patient is 0.61.

Table 3: Sample size to detect various reductions in AUC-MAP<65 for HPI vs control Recommended sample size in the 35% attempted reduction column is total N=213

Assume control group median [q1,q3] = 24 [1, 121]; mean (SD) =80 (127); zeros = 27% Power=80%, alpha=0.05, no interim analyses

Attempted	10%	20%	30%	35%	40%	50%	60%	70%
Reduction*:	(8)	(16)	(24)	(28)	(32)	(40)	(48)	(56)
% of control mean								
(mmHg x min)								
Achieved reduction								
HPI group Median	16	8	0.5	0	0	0	0	0
Ratio of medians	.67	.33	.02	0	0	0	0	0
HPI group mean	75	70	66	64	62	58	55	51
Ratio of means	.93	.87	.81	.79	.77	.72	.68	.64
Total N	1511	460	261	213	187	140	115	93
WMW prob (P')	.54	.57	.60	.61	.62	.63	.65	.67
1/ WMW odds	.85	.74	.67	.64	.62	.58	.54	.50

^{*}Attempted Reduction: Amount of attempted reduction in AUC-MAP<65 for each observation, listed as percent of control MEAN and in actual units. Achieved individual reduction was less (or even zero) in some cases since true value for an individual cannot go below zero.

HPI median: median of HPI group after the induced shift

Ratio of medians: HPI median / control median (24 mmHg x min)

HPI mean: mean of HPI group after the induced shift

Ratio of means: HPI mean / control mean (80 mmHg x min)

WMW prob (P'): Wilcoxon-Mann-Whitney probability (P'). Equal to a c-statistic from logistic regression. Probability that randomly chosen HPI patient has lower AUC-MAP<65 compared to random control patient. P' = 0.50 under null hypothesis (i.e., would be achieve by guessing), and 1.0 is perfect discrimination.

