An initial training meeting before study enrollment will ensure reliability and consistency in the use of Acumen HPI software and written standard operating procedures (SOPs). At least 80% of the data will be independently audited to confirm consistency among patient records, study data sheets, and the main database. Data will be maintained on a custom-designed Access or SQL relational database. Data will be transcribed by separate sets of investigators. We have programmed and used similar password-protected databases in our previous major outcome trials. Trial management will be coordinated from the department of Outcomes Research, Cleveland.

HUMAN SUBJECTS RISKS AND PROTECTION

The Cleveland Clinic Institutional Review Board will approve the proposed trial. Written informed consent will be obtained from each participating patient. Patients who decline to participate will be given regional or general anesthesia and analgesia per their preference and that of their attending anesthesiologist; research data will not be collected from these patients.

1. Human Subjects Involvement and Characteristics:

The executive committee which will not otherwise be involved in day-to-day aspects of the protocol, will evaluate all results from the proposed trial. This committee, along with the IRB, will have exclusive authority to stop the studies either because the hypotheses have been confirmed, denied, or because adverse events are detected. It will be the responsibility of this committee to alert the IRB at each participating institution to any untoward toxicity in one of the study groups.

2. Sources of Material

Data obtained routinely for clinical purposes will be used in this study. Such data include: 1) anesthetic dose and safety monitoring; 2) fluid balance and transfusion requirements; 3) postoperative nausea and vomiting; 4) details of surgery; and 5) morphometric and demographic information. Postoperative outcomes will be retrieved daily from the patients' charts.

3. Potential risks to Subjects

Monitoring and Data Collection: Some data obtained routinely for clinical purposes will be used in this study. Such data include: anesthetic concentration and safety monitoring (end-tidal gases, arterial blood pressures, oxygen saturation, esophageal temperatures, intraoperative arterial blood gas samples, etc.), fluid balance, and urine volume. Recording these data is clinical standard and introduces no additional risk.

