Two copies of the Informed Consent form will be made. One copy remains in the patient's chart, another copy will be given to the patient, and the original will be filed with the case report form. The original consent will thus be available to the investigators, their staff, study monitors, and each institution's IRB.

5. Protection against Risks

All interviewers will undergo training by our consenting study coordinators and must demonstrate a high level of proficiency before being certified to interview subjects. Research fellows and study coordinators will be trained in all aspects of the study. Procedures used to assure the integrity of data include: (1) quarterly external audits by Outcomes Research staff, (2) data entry procedures following standard operating procedures (SOPs), and (3) data queries and resolution processes following SOPs. Frequent interaction among members of the study Executive Committee (PI, co-investigators, consultants), RAs, and others as necessary, will maintain overall quality assurance. They will meet or have conference calls at least quarterly throughout the data collection period, and as necessary thereafter.

The executive committee will evaluate all results from the proposed trial at least yearly, but more often if the Committee deems it necessary. It will be the responsibility of this committee to alert the IRB *via* letter to any untoward toxicity in one of the study groups. This committee, along with the IRB, will have exclusive authority to stop the study either because the hypotheses have been confirmed or denied, or because adverse events are detected. The executive committee will operate under guidelines published on the NCI web site.

6. Collaborating Sites

Single center

7. Gender and Minority Inclusion

We have no reason to believe that the effects of hemodynamic management on outcome are related to race or ethnicity. We will consequently include patients of all races and ethnicities and make a special effort to include minorities. We assume that our study population will reflect the patient population of each participating health system. In Cleveland, our participants will be roughly 10% Hispanic and 15% African American.

8. Inclusion of Children

Children will be excluded from the proposed studies.

REFERENCES

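### The executive committee may stop the trial because its hypotheses are settled, with no look schedule or boundary, while N=213 and the 5% error rate assume no interim analyses

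*Combined protocol and SAP*

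**What the plan says.** **Stopping authority.** It is given twice under Human Subjects Risks and Protection. Item 5 (Protection against Risks) states: "This committee, along with the IRB, will have exclusive authority to stop the study either because the hypotheses have been confirmed or denied". Item 1 (Human Subjects Involvement and Characteristics) says the committee and the IRB may "stop the studies either because the hypotheses have been confirmed, denied, or because adverse events are detected". In both places adverse events are a separate ground, so the hypothesis ground concerns efficacy or futility.

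**Frequency.** Item 5: "The executive committee will evaluate all results from the proposed trial at least yearly, but more often if the Committee deems it necessary". The Trial Summary gives "Anticipated enrollment period: 12 months".

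**Governing rule.** The only one named is: "The executive committee will operate under guidelines published on the NCI web site". No document, boundary or error allocation is identified.

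**Statistical design.** The header of Table 3 (Sample Size Considerations) reads "Power=80%, alpha=0.05, no interim analyses". Data Analyses specifies a two-tailed Wilcoxon-Mann-Whitney test of the primary outcome and no interim test. The sample size summary describes the larger study's calculation as "based on 90% power and incorporating interim analyses".

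**Blinding.** "Principal investigators, co-investigators and the data analysis team will be blinded for the treatment groups". The Executive committee section places the principal investigator and the lead statistician on the committee.

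**The concern.** A committee that can look at results whenever it wishes, and stop because the hypothesis is confirmed, has an efficacy stopping rule without a boundary. If it compares the arms early and stops at an unadjusted 0.05, the false-positive rate of the primary test exceeds 5%, and the effect estimate from a stopped trial is biased upward. Stopping because the hypothesis is denied does not inflate type I error, but it reduces power below the planned 80%.

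The larger study's sample size allowed for interim analyses and this one does not. Leaving them out here was therefore a choice, and the stopping authority does not fit it. If the trial did stop early, no reader could say what error rate applied. Even if it ran to completion, undocumented comparative looks would leave the final p-value open to challenge.

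**Working it through.** **1. Is N=213 a single-look sample size?** Inputs from Sample Size Considerations: two-sided alpha 0.05, power 80%, Wilcoxon-Mann-Whitney probability P' = 0.61, 1:1 allocation. Noether's formula, with c the fraction allocated to one arm, is

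N = (z₀.₉₇₅ + z₀.₈₀)² / [12 c(1−c)(P' − 0.5)²] = (1.960 + 0.842)² / [12 × 0.25 × 0.11²] = 7.849 / 0.0363 = 216.2.

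This is within 3% of 213. Rounding of P' alone (0.605 to 0.615) spans 237 down to 198. A one-sided test would give 170, and 90% power would give 289. So 213 is a fixed, single-look, two-sided design at 80% power, with nothing added for interim testing.

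**2. Type I error with unadjusted looks.** The documents give neither the number of looks nor the threshold for calling a hypothesis confirmed. Both are assumptions here: the trial rejects if |z| > 1.96 at any look. The values come from recursive numerical integration of the score process.

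| Looks before the final analysis | Overall two-sided type I error |
|---|---|
| None (strictly yearly review, 12-month enrolment) | 5.0% |
| One, at 25% of the data | 9.1% |
| One, at 50% | 8.3% |
| One, at 75% | 7.3% |
| One, at 90% | 6.5% |
| Two, equally spaced | 10.7% |
| Three, equally spaced (for example quarterly over 12 months) | 12.6% |

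As a check on skewed data with many zeros, 40,000 trials were simulated with 107 per group and the tie-corrected test. Both arms came from a distribution with 27% zeros, median 24 and upper quartile 121. Its upper tail had to be assumed; its mean was 89 and SD 139, against the stated 80 and 127. Results were 5.1% with no interim; 9.3%, 8.3% and 6.6% with one at 25%, 50% and 90%; 10.7% with two; and 12.8% with three (standard error at most 0.17 percentage points).

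**3. Chance of an early stop, and bias.** Under the design effect the final z has mean 1.960 + 0.842 = 2.802. At half the data its mean is 2.802 × √0.5 = 1.981. The chance of crossing 1.96 is Φ(1.981 − 1.960) = Φ(0.021), about 51%. Among trials that stop, the mean z is 1.981 + φ(0.021)/0.508 = 1.981 + 0.785 = 2.766. The standardised effect is then overestimated by 2.766/1.981, about 1.40-fold.

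**4. Power lost by stopping because the hypothesis is denied.** Take one look at half the data, with power 80% if there is no look. Stopping when z < 0 gives power 79.7%; stopping when z < 1 gives 73.6%.

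**5. Cost of a proper boundary.** O'Brien-Fleming boundaries with equally spaced looks, again taking power as exactly 80% at N=213 for a single look:

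| Interims | Power at N=213 | Inflation factor | N for 80% power |
|---|---|---|---|
| 1 | 79.7% | 1.008 | 214.7, so 215 |
| 2 | 79.3% | 1.017 | 216.7, so 217 |
| 3 | 79.1% | 1.024 | 218.1, so 219 |

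For one interim at half the data, the nominal two-sided levels are 0.005 at the interim and 0.048 at the end.

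**The case against.** The strongest reply is that no interim look is actually planned. Table 3 says so, Data Analyses describes one final test, and yearly review of a trial expected to enrol in 12 months may produce no true interim look. The governance wording also looks carried over: item 1 refers to studies in the plural and to an IRB at each participating institution, although the trial is single-center. Blinding of the investigators and analysis team would hinder an informal stop, and the NCI guidelines may contain stopping rules.

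Part of this stands. At the minimum review frequency, with enrolment on time, the error is 5.0%. Every higher figure assumes that the committee uses its discretion, or that accrual overruns, and that it tests at 0.05. The wording is also weak evidence that anyone intends an efficacy look.

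It does not remove the contradiction:

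- Yearly is a floor, 12 months is only anticipated, and the protocol has the executive committee members meet or confer at least quarterly.
- A comparison of coded arms spends alpha just as an unblinded one does. The committee is also expected to report toxicity in one of the study groups, which requires data by arm. The blinding text is therefore a further point to reconcile, not a safeguard.
- A reference to unspecified guidelines cannot be relied on to control the error rate.
- Carried-over text still confers authority while it stands.

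**Conclusion.** The concern holds and should be corrected before any comparative review. The stopping authority in items 1 and 5 contradicts the single-look design behind N=213, and nothing in the documents limits the resulting error. The contradiction is certain because it is in the text. The size of the inflation is conditional: none if there is no comparative look before the end, 6.5% to 9.1% for one unadjusted look depending on its timing, and 10.7% or 12.6% for two or three. These figures assume a two-sided 0.05 test at each look.

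**What to change.** **Preferred.** In items 1 and 5 of Human Subjects Risks and Protection, delete the ground of stopping because the hypotheses are confirmed or denied, and keep the adverse-event ground. State in Data Analyses that there is no efficacy or futility interim analysis. State also that committee review uses pooled outcome data, with adverse events shown by coded arm, so that it agrees with the Blinding section. The cost is a wording amendment with no extra patients or staff. The sponsor gives up an ad hoc option to stop early, and the stated 5% and 80% then describe the trial as run.

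**If an efficacy look is wanted.** Prespecify the number and timing of looks and an O'Brien-Fleming boundary. Remove the statement in Table 3 that there are no interim analyses. Then either report the power at 213 (79.7%, 79.3% or 79.1% for one, two or three interims) or raise N to about 215, 217 or 219. Say who sees the comparative results, since the present committee includes the principal investigator and the lead statistician.

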APPENDIX

1. Description of hemodynamic parameters

- MAP= mean arterial pressure. Average systemic arterial blood pressure.
- CO= cardiac ouput. Volume of blood ejected per minute from the heart into the systemic circulation measured in liters per minute.
- PR=pulse rate= heart rate
- SV = stroke volume. Amount of blood ejected from the ventricles with each contraction.
- SVV=stroke volume variation. Stroke volume variation is the percent difference between maximum and minimum stroke volume. A SVV>12% means the patient is fluid responsive. Fluid responsiveness means the cardiac output will increase when fluids are administered.
- SVR=Systemic vascular resistance. A derived measure of impedance to blood flow from left ventricle (afterload). Formula: SVR = (MAP CVP) x 80 /CO (dynesec/cm5) where: CVP Central Venous Pressure
- dP/dt = a measure of left ventricular contractility from an arterial pressure waveform, for contractility. It is the maximal first derivative with respect to time of arterial pressure waveform. Formula: dP/dt = max(P[n+1]-P[n]), for n=0 to N-1 where: P[n] current sample of the arterial pressure signal, mmHg N total number of samples in a given cardiac cycle
- Eadyn= Dynamic elastance. Dynamic arterial elastance is the ratio of pulse pressure variation and stroke volume variation (PPV/SVV). It is an estimate of arterial elastance

2. Quality of recovery questionnaire (QOR-15)

QoR-15 Patient Survey

	Q.C	/K-131	ati	CII	. 0	41 V	-y							
Dat	te://								S	tudy	/#:_			
Pre	eoperative										Pos	tope	rati	ve
PA	RT A													
Но	w have you been feeling in the	last 24	hou	ırs?	•									
	(0 to 10, where: 0 = none of	f the time	e [po	oor]	and	10	= all	of t	he t	ime	[exc	eller	nt])	
1.	Able to breathe easily	None of the time		1	2	3	4	5	6	7	8	9		All of the time
2.	Been able to enjoy food	None of the time		1	2	3	4	5	6	7	8	9		All of the time
3.	Feeling rested	None of the time		1	2	3	4	5	6	7	8	9		All of the time
4.	Have had a good sleep	None of the time		1	2	3	4	5	6	7	8	9		All of the time
5.	Able to look after personal toilet and hygiene unaided	None of the time		1	2	3	4	5	6	7	8	9		All of the time
6.	Able to communicate with family or friends	None of the time		1	2	3	4	5	6	7	8	9		All of the time
7.	Getting support from hospital doctors and nurses	None of the time		1	2	3	4	5	6	7	8	9		All of the time
8.	Able to return to work or usual home activities	None of the time		1	2	3	4	5	6	7	8	9		All of the time
9.	Feeling comfortable and in control	None of the time		1	2	3	4	5	6	7	8	9		All of the time
10.	Having a feeling of general well-being	None of the time		1	2	3	4	5	6	7	8	9		All of the time
PA	RT B													
Ha	ve you had any of the following	g in the	last	t 24	hοι	ırs?								
	(10 to 0, where: 10 = none	of the tin	ne [e	exce	ellen	t] ar	nd 0	= al	l of	the	time	[poo	or])	
11.	Moderate pain	None of the time		9	8	7	6	5	4	3	2	1		All of the time
12.	Severe pain	None of the time		9	8	7	6	5	4	3	2	1		All of the time
13.	Nausea or vomiting	None of the time		9	8	7	6	5	4	3	2	1		All of the time
14.	Feeling worried or anxious	None of the time		9	8	7	6	5	4	3	2	1		All of the time

The quality of recovery score (QoR)-15 questionnaire.

15. Feeling sad or depressed

3. The POMS (Grocott MP et al)

Morbidity type	Criteria	Source of data					
Pulmonary	ary Has the patient developed a new requirement for oxygen or respiratory support.						
		Treatment chart					
Infectious	Currently on antibiotics and/or has had a temperature of >38°C in the last 24 hr.	Treatment chart					
		Observation chart					
Renal	Presence of oliguria <500 mL/24 hr; increased serum creatinine (>30% from preoperative level); urinary catheter in situ.	Fluid balance chart					
		Biochemistry result					
		Patient observation					
Gastrointestinal	Unable to tolerate an enteral diet for any reason including nausea, vomiting, and abdominal distension (use of antiemetic).	Patient questioning					
		Fluid balance chart					
		Treatment chart					
Cardiovascular	Diagnostic tests or therapy within the last 24 hr for any of the following: new myocardial infarction or ischemia, hypotension (requiring fluid therapy	Treatment chart					
	>200 mL/hr or pharmacological therapy), atrial or ventricular arrhythmias, cardiogenic pulmonary						
	edema, thrombotic event (requiring anticoagulation).						
Neurological		Note review					

Morbidity type	Criteria	Source of data			
	New focal neurological deficit, confusion, delirium, or coma.	Patient questioning			
Hematological	Hematological Requirement for any of the following within the last 24 hr: packed erythrocytes, platelets, fresh-frozen plasma, or cryoprecipitate.				
Wound	Wound Wound dehiscence requiring surgical exploration or drainage of pus from the operation wound with or				
	without isolation of organisms.	Pathology result			
Pain	Pain New postoperative pain significant enough to require parenteral opioids or regional analgesia.				
		Patient questioning			

4. Non-cardiac surgeries routinely requiring invasive monitoring:

Vascular surgeries: Bypasses for Peripheral Arterial Disease, Carotid Endarterectomy, AAA repair (open or endovascular)
Spinal surgeries: thoracolumbar fixations/instrumentation for scoliosis
Orthopedic procedures: Femoral fracture fixation
Head & Neck procedures: Laryngectomies, flap reconstructive surgeries
Thoracic Surgery: VATS, lobectomies, pneumonectomies, mediastinal tumor
excision, Esophagectomy, Redo Nissen fundoplication
GI & Colorectal surgery: Total proctocolectomy, Whipple's procedure,
laparoscopic adrenalectomies

Genitourinary procedures: Cystectomies with creation of ileal conduit, Partial nephrectomies

Liver surgeries: Liver resections

Gynecologic procedures: Staging for ovarian Cancer, Radical Hysterectomies
